Aim 1: Determine if long-term AFU usage provides sustained reductions in PM2.5 exposure and persistent improvements in cardiometabolic outcomes. We propose a randomized double-blind 2-way crossover study (AFUs bedroom- vs. sham filtration) in 50 adults living in a low-income senior residence impacted by roadway pollutants. We posit that compared to sham, AFU use *long-term* (4-week) periods will **(1a)** lower resting morning BP (*primary outcome*), **(1b)** reduce indoor PM2.5 and 24-hr personal PM2.5 exposures, and **(1c)** improve secondary health outcomes: 24-hr and nocturnal BP, 24-hr and nocturnal aortic hemodynamics (BP, augmentation index), and insulin sensitivity.

Aim 2: Determine if nocturnal PM2.5 exposure reduction alone improves cardiometabolic outcomes. We posit that compared to sham, bedroom-only AFU use will **(2a)** lower resting morning BP. We further posit that **(2c)** 24-hr personal PM2.5 exposure and **(2d)** secondary health outcomes will improve – particularly nocturnal BP (a powerful

predictor of CV events)³³⁻³⁵.

Aim 3: Demonstrate the key role of adrenal activation as a novel mechanism explaining PM2.5-induced cardiometabolic effects. Recent data suggest PM2.5 provokes hypothalamic-pituitary-adrenal axis (HPAA) activation³². We posit **(3a)** AFU will reduce adrenal activation (comprehensive assessment by blood steroidomic profiling) after 4 weeks. Steroids with glucocorticoid and mineralocorticoid activity will be shown **(3b)** to be mediators of PM2.5-induced BP changes & insulin resistance.

PM2.5 is a leading risk factor for mortality. Our proposal, which will help validate the benefits of novel strategies to employ AFUs in an elderly vulnerable population living in a non-traditional setting, is directly responsive to the Program Announcement (PA-18-142), and is of global public health importance. Positive results would form a key part of the evidence base required to promote more wide-scale AFU use. In the long term, given the low cost and burden, AFU use could be up-scaled to help protect diverse populations across the world.

RESEARCH STRATEGY

SIGNIFICANCE

PM2.5 is a major contributor to the global epidemic of cardiometabolic diseases.

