We successfully completed the RAPIDS clinical trial protocol on schedule (R01 NR014484)21. As with all clinical trials, we had to await full completion prior to analysis, which has limited the number of papers for submission at this time. We have nonetheless been highly productive. Our main results (Specific Aim 1) are in press in a top-tier medical journal³⁰ (“Publication List” #1). We also published a review on strategies to reduce PM2.5 exposures²¹ (“Publication List” #2). Our third manuscript, accepted for publication, characterizes numerous details of *personal* PM2.5 exposure reduction by AFUs³¹ (“Publication List” #3). Two further manuscripts are currently in preparation. Major findings of these manuscripts are briefly discussed in below.

The specific aims for the original RAPIDS study were: (1) to determine whether filter-based interventions are capable of reducing PM2.5 exposures and thereby improve clinically-relevant intermediate CV health endpoints in a senior-citizen facility; (2) to identify which measurement of PM2.5 – outdoor, indoor or personal – is most closely associated with the CV health outcomes under three different filtration scenarios in a senior-citizen residential facility; and (3) To determine whether filter-based intervention reduce exposures to specific outdoor sources of PM2.5 and thereby improve the CV health endpoints in a senior-citizen residential facility.

Main results: We enrolled 40 nonsmoking elderly adults living a senior facility in midtown Detroit into a randomized double-blind crossover study with daily CV health outcomes and PM2.5 exposure measurements. There were no activity restrictions (e.g., window closure requirements) during the study. Participants were exposed to three blinded 3-day-long scenarios separated by one-week washout periods: unfiltered ambient air

Figure 1: Multiple pathways of HPAA activation due to PM_{2.5} exposure

[figure not shown]

Figure 2: AFUs lowered evening-night personal PM_{2.5} exposures by the greatest extent. During night alone (10pm-8am), 62% of the total 24-hr exposure reduction occurred³¹.

[figure not shown]
[figure not shown]

Figure 3: Any AFU usage lowered 3-day average BP levels³⁰.

Figure 4: AFU use and reductions in central aortic AP (augmentation pressure) and PP (pulse pressure)³⁰.

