Washout period: Participants will undergo a 1 or 2-week washout period without restrictions on activities (including overnight travel). No AFUs will be in participant's apartments during this time. We have shown in RAPIDS that a 1-week washout period is adequate, with no evidence for a carryover effect from the previous intervention on endpoints (BP, PM2.5 exposures). There was no statistically significant effect (interaction, confounding) from the order of the intervention on the results³⁰. PM2.5 exposures and BP returned to baseline after one week.

Block 2 (crossover phase): Participants will undergo the same protocol as during Block 1, the only difference being that on week 1/visit day 1 of both blocks, the AFUs will be set to different modes (active vs. sham) from prior blocks(in randomized order).

Retention plan: Based on our experience with RAPIDS, we do not anticipate retention problems. During weeks 2 and 3, investigators will contact each participant at least twice per week (phone, email, or in-person) to assure continued participation and compliant usage of AFUs, and to address any study problems.

Timeline: In RAPIDS, only 1/41 participants dropped out after enrollment. However, given the longer duration of this protocol, we intend to be realistically conservative in our estimates for RAPIDS-2. We will allow for a 10% dropout rate and thus plan to enroll 55 people to meet our goal of n=50 participants completing the entire study.

Aim 1: Determine if long-term AFU usage provides sustained reductions in PM2.5 exposure and persistent improvements in cardiometabolic outcomes.

Aim 2: Determine if nocturnal PM2.5 exposure reduction improves cardiometabolic outcomes.

Aim 3: Demonstrate the key role of adrenal activation as a novel mechanistic pathway explaining PM2.5-induced cardiometabolic effects.

Experimental Procedures and Protocols

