
Table 1: List of Study Endpoints

Health Endpoints	Endpoint designation
Unattended automated systolic BP 4-day average (Tues-Fri) in weeks 1 and 4	Primary study outcome (Aims 1a, 2a/2b) Study is a priori powered for this endpoint
24-hour BP levels & aortic hemodynamics	Secondary endpoints (Aims 1c & 2d)
Insulin sensitivity (HOMA-IR)	Secondary endpoint (Aims 1c & 2d)
Adrenal steroid panel (blood)	Secondary mechanistic endpoints (Aims 3a/3b)
Exposure Endpoints	
24-hr personal PM _{2.5} (filter-gravimetric mass)	Primary exposure outcome (Aims 1b, 2c)
Daily indoor PM _{2.5}	Primary exposure outcome (Aims 1b)
Black carbon, hourly personal PM _{2.5} levels	Secondary exposure endpoints

modes. In RAPIDS, no participant complained or required the AFU to be stopped due to noise³⁰. The AFUs will run in the same blinded mode continuously for the entire 4-week block. During the washout periods, the offsite investigator will

remove or install the HEPA filters in the AFUs prior to starting the next block. The HEPA filters are rated to be effective for the entire 8 weeks of active usage and will not need to be replaced.

Protocols for cardiometabolic health endpoints

Home BP: This BP measurement will be the primary outcome (Table 1). The **rationale** is that high BP is a well-established predictor of CV risk⁶⁸⁻⁷¹, the leading risk factor for global mortality³, increases due to short-term PM2.5 exposure^{5-8,36-56}, and was shown by our RAPIDS study³⁰ to be reduced by AFUs. Unattended automated BP more accurately reflects 24-hour BP, is less impacted by variability and the white coat effect and is superior to the standard technique as a predictor of hypertensive complications⁷¹. The repeat-measured morning BP average using the BpTRU device was the primary outcome in RAPIDS³⁰, thus it is important to use this same method in this renewal project.

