Enrollment: Interested residents will call the study research coordinator. Study inclusion/exclusion criteria will be reviewed (no changes). All subjects must attest to be non-smokers living in non-smoking household. Consents will be left at the office or subjects will be emailed or mailed the consent form and subjects will be given ample time to review the consent and consider their participation independently. Study team will review the consent document over the telephone just as they would during a face to face meeting. Signature will be obtained on the consent form and provided to the study staff via mail or left for pickup by study staff in the same manner as equipment is dropped off with no contact. This cohort is unlikely to benefit from electronic consenting procedures based on the lack of internet access, the poor internet provided by Carpenter Place, the willingness of the participants, and the added burden it would place on this older population of subjects participating in a low risk study.

Study Flow: The modified trial will be conducted per the original design except for no face-to-face interactions between research staff and subjects and the protocol has been simplified. Subjects will be assigned a research ID number. They will be randomized in a blinded fashion to either active vs sham PAC use for intervention block 1. After completing block 1, they will washout for 1 week and then crossover to block 2 and undergo the same trial randomized to the alternative PAC intervention (sham vs active).

BLOCK 1 (2)													Washout	
	Week 1 (6)					Wk 2-3 (7-8)		Week 4 (9)						
	Day					Day								
	1 M	2 T	3 W	4 Th	5 F			1 M	2 T	3 W	4 Th	5 F		
PAC INTERVENTION (2 limb x-over)														
Randomized PAC	↓	x	x	x	x	----->	x	x	x	x	x	↑		
TESTING														
Home BP: AM		✓	✓	✓	✓			✓	✓	✓	✓	✓		
PM		✓	✓	✓	✓			✓	✓	✓	✓	✓		
PM MONITORING														
In-room PM (Purple Air)	↓	x	x	x	x	----->	x	x	x	x	x	↑		
Personal PM (PDR1500)											↓	↑		

↓ = start; x = continue; ↑ = stop; ✓ = check BP; -----> = continues throughout period

Week-1/day-1: PAC Intervention/bedroom PM monitoring: Start in subject's bedroom at 9 am

Home BP: am= when first wake up in bedroom; pm=just before going to sleep in bedroom

Personal PM monitoring: Wear/have on person during daytime. Put by bedside at night-time.

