Week-1/day-1: Staff will drop off the study equipment between 8-9 AM. The equipment will all have been cleaned and sterilized beforehand. It includes a home BP monitor (and instructions), the blinded-randomized (active or sham) indoor PAC (and instructions for its use), and a PurpleAir monitor (and instructions for positioning and use).

At 9 AM, the subject will position the PAC in their bedroom per instructions, plug it in and turn it on. They will keep the PAC running at the highest tolerated setting (per protocol and instructions) and keep it running throughout weeks 1-4 in their bedroom. The subject will also plug in the PurpleAir and position it at least 6 feet away from the PAC in their bedroom per instructions (off the floor on a table). They will make sure it is running for continued air pollution monitoring throughout weeks 1-4 in their bedroom per provided instructions.

Home BP monitoring: The subject will measure home BP upon awakening in the morning and just before bedtime on week-1 (days 2-5 = Tuesday through Friday) and on week-4 (days 2-5 = Tuesday through Friday). They will follow instructions for home BP monitoring without change from original protocol. They will sit 5 minutes prior to measurement with right arm resting at heart level on a table. They will measure BP in triplicate on right arm. The Omron-10 series will be set to measure BP in triplicate at 1-minute intervals. The device stores all time-stamped BP readings and subjects will record on a log for safekeeping of data.

Subject reminders: The study coordinator will contact the subject week-4/day-1 (mon) to remind the subject to begin home BP monitoring on week-4/day-2 for the next 4 days.

Personal PM-monitoring (week 4): The study coordinator will call the subjects and Carpenter Place staff to remind them about personal PM monitoring which will occur on week-4/day-4 starting at 9-AM and continue for 24-hours through day-5 at 9-AM. The coordinator will drop off the pDR-1500 (with instructions for use) before 9-AM on day-4 at the front lobby of Carpenter Place. The subject will pick-up the monitor, turn it on, and wear it (on belt or strap) for the next 24-hours as per instructions. During sleep or showering the monitor can be kept close to their person (bedside).

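### Aim 2 credits night-time PM2.5 reduction, but the design tests only continuous bedroom filtration versus sham, the same contrast as Aim 1a

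*Combined protocol and SAP*

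**What the plan says.** In the Specific Aims, Aim 2 is headed "Determine if nocturnal PM2.5 exposure reduction alone improves cardiometabolic outcomes". Where the aims are restated after the Timeline paragraph, the heading becomes "Determine if nocturnal PM2.5 exposure reduction improves cardiometabolic outcomes". The restriction to night alone is gone, but the benefit is still tied to night-time reduction. The hypotheses under the first heading are framed by device: "We posit that compared to sham, bedroom-only AFU use will" lower morning BP (2a), with 24-hour personal PM2.5 as 2c and secondary health outcomes as 2d. No 2b is listed there.

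On running time, the AFU intervention section says "The AFUs will run in the same blinded mode continuously for the entire 4-week block" and adds a power meter to confirm it. The Protocol Modifications (Week-1/day-1) tell the subject to "keep it running throughout weeks 1-4 in their bedroom".

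On conditions, Aim 1 describes a "randomized double-blind 2-way crossover study (AFUs bedroom- vs. sham filtration" comparison. Study Flow in the Protocol Modifications says "They will be randomized in a blinded fashion to either active vs sham PAC use for intervention block 1", with crossover to the other mode in block 2.

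Study Power and Analysis Plans gives power for Aim 1a (bedroom unit versus control, at 4 days and at 4 weeks), claims similar power for Aim 2a (bedroom-alone unit versus control), and calls the study powered for 1a, 2a and 2b. The mixed model tests a2 = 0 for Aim 1a, a3 = 0 for Aim 2a, and a2 = a3 for Aim 2b. Multiplicity is handled by Holm, without a count of hypotheses.

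**The concern.** An aim that names night-time reduction as the cause needs a contrast in which night-time reduction differs and daytime reduction does not. A unit running around the clock, compared only with sham, does not supply one. A positive result could then be read under the Aim 2 heading as evidence about night-time exposure, when it is evidence about a device left on continuously in one room.

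The second problem is in the analysis plan. Two aims, two coefficients and an equality test are specified for a design with a single treatment contrast. An analyst cannot follow that plan as written, and a reader could take one finding as two.

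**Working it through.** The plan gives no figure for this point to reproduce, so the check sets the sections side by side.

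**1. Can night be separated from day?**
- Conditions: active or sham, one of each per participant (Specific Aims; Study Flow in the Protocol Modifications).
- Running time in either mode: the whole block (Block 1, Week 1/day 1; AFU intervention; Protocol Modifications, Week-1/day-1).
- Active minus sham therefore equals the effect of whatever night reduction plus whatever day reduction the unit produces. No condition varies one without the other.
- The plan itself expects more than a night effect. Hypothesis 2c concerns 24-hour personal exposure, and the Significance section on the bedroom-only strategy anticipates a fall in overall 24-hour exposure.

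**2. Are Aims 1a and 2a different tests?**
- Same contrast: bedroom unit versus control in both power statements.
- Same outcome: Table 1 assigns one primary outcome, in weeks 1 and 4, to 1a, 2a and 2b together.
- They are therefore one hypothesis at each time point.

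**3. Can the model be fitted?** It contains an intercept a0, a2·I(B = 1) and a3·I(B = 2). The text does not say which condition each value of B denotes.
- If B follows the block labels in the power section (bedroom-alone is block 2, control is block 3), B = 1 never occurs. The a2 column is all zeros, and the test assigned to Aim 1a has no data.
- If B = 1 is active and sham is the reference, the a3 column is all zeros, and the test for Aim 2a has no data.
- If B = 1 and B = 2 are the two existing conditions, I(B = 1) + I(B = 2) = 1 on every row, which duplicates the intercept. Only a2 − a3 is estimable, and that is again active versus sham.

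Under every coding there is one estimable treatment contrast, not three tests.

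**4. Effect of listing it twice under Holm.** Assume alpha = 0.05.
- One time point: one hypothesis, threshold 0.05. Entered twice, the first threshold is 0.05/2 = 0.025.
- Two time points: two hypotheses, first threshold 0.05/2 = 0.025. Each entered twice, 0.05/4 = 0.0125.

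**5. Where the extra terms probably come from.** Several passages fit a three-condition design: the Trial Overview's reference to two active strategies, two-room placement in AFU intervention, Blocks 1-3 in Blood draws collection, and block 3 as control in the power section. The 14-week period in exclusion criterion 5 equals three 4-week blocks plus two 1-week washouts (12 + 2). The current trial is described as 10 weeks (2 × 4 plus a washout of up to 2). This origin is an inference, but the contradiction is plain on the page.

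**The case against.** The strongest reply is that only a heading is at fault. Hypothesis 2a, bedroom-only unit versus sham, is exactly what the crossover estimates, and the body of the plan presents a practical device strategy. That stands: the active-sham estimate is valid, and nothing in the analysis section commits the sponsor to a night-only conclusion. It does not save the aim's stated conclusion, and it does not touch the a2/a3 problem.

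A second reply is that BP on waking reflects the preceding night. The plan's own account weakens this. The Significance section describes BP responses that lag exposure by 1-3 days and last several days, so a morning reading carries earlier day and night exposure.

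Several stronger readings are tempting but unsupported:
- *That 38% of the benefit would be wrongly credited to night.* Figure 2 reports that at night "62% of the total 24-hr exposure reduction occurred", and 100% − 62% = 38%. But that trial ran a second unit in the main living space, and the figure is a share of exposure reduction, not of BP effect. No share is given for a single bedroom unit.
- *That the unit cleans the whole apartment.* It is rated for spaces up to 310 square feet, and the apartment is 576. The daytime reduction is unknown.
- *That duplication inflates type I error.* Holm becomes stricter, as shown above.
- *That dropping ambulatory BP causes the problem.* It removes the night-time outcome, but keeping it would not separate day from night exposure.
- *That restoring a two-room condition would cure it.* Those units also run continuously.

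**Conclusion.** The point holds in this form. The design identifies the effect of continuous bedroom-only filtration versus sham. It does not identify the effect of night-time PM2.5 reduction alone, because that reading requires a zero daytime reduction, which nothing in the plan assures. Aims 1a and 2a are one contrast, Aim 2b has no separate content, and the model as written cannot deliver the three tests for which the study is said to be powered.

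No numerical size can be put on the misattribution, because the documents give no day/night share for one bedroom unit. The multiplicity cost is a halving of the first Holm threshold, assuming alpha 0.05 and each test entered twice. The primary active-sham estimate is unaffected. The conclusion rests on the two-condition crossover being the governing design, as both the Specific Aims and the Protocol Modifications state.

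**What to change.** - Reword Aim 2, in both places, to the effect of continuous bedroom-only filtration versus sham, and drop the conclusion about night-time reduction alone.
- Replace a2 and a3 with one active-versus-sham treatment coefficient, say how it is estimated at week 1 and at week 4, and delete Aim 2b from Table 1, the power text and the model.
- State that 1a and 2a are one hypothesis at each stated time point, and list the Holm family on that basis.
- Reconcile the leftover multi-condition text in Trial Overview, AFU intervention, Blood draws collection, the power section and the model.
- Report the day and night shares of the personal PM2.5 reduction descriptively, from the hourly pDR-1500 windows already planned. After the modification these cover one 24-hour period per block. They can make a night-time reading more or less plausible but cannot test it. The PurpleAir sensor now sits in the bedroom, so its daytime readings are not personal exposure when the subject is elsewhere.

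The cost is text in the aims, Table 1 and the analysis plan, plus one descriptive table. No new data or participants are needed.

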3.3.2. STUDY DESIGN AND EXECUTION

We will use well-validated methods with which we have extensive experience through our initial RAPIDS project³⁰ (R01 NR014484) and in prior studies³⁶⁻⁵⁶ to characterize PM2.5 exposures and health responses. The rationale and design/methods of our proposed renewal trial (RAPIDS-2), primary outcome (systolic BP), study power and AFU intervention are well-justified by our initial project findings.³⁰ We have also intentionally designed the trial to minimize risk and burden to the elderly participants. The protocol will be conducted entirely within a senior living facility and will evaluate clinically informative yet minimally-invasive endpoints (Fig. 5). Our design using a randomized double-blind cross-over trial and our method for obtaining our primary outcome (the average systolic BP measured 4 days in a row by unattended automated 5 repeated measurements) are intended to address NIH's Rigor and Reproducibility guidelines. The trial is principally designed and powered to validate the real-world clinical cardiometabolic benefits of AFUs (Aims 1 and 2). While we will explore a novel mechanistic underpinning (Aim 3), we recognize that invasive procedures (that might provide more detailed biological understandings) are not feasible in this setting and could jeopardize the success of Aims 1 and 2. Thus, we designed Aim 3 to be informative but also as unobtrusive as possible. While our secondary outcomes have never been evaluated in an AFU trial (including steroidomic profiling), we have extensive experience with each endpoint and thus will have no difficulties in adapting them into the study protocol.

Trial Overview

We propose a randomized double-blind placebo-controlled (sham filtration) crossover trial comparing the effectiveness of bedroom-only AFU use to reduce personal PM2.5 exposures and improve cardiometabolic health (Fig. 5). The health benefits (primary outcome: resting BP) of both active AFU strategies will be evaluated over acute (4-day) and long-term (4-week) periods in 50 nonsmoking elderly adults living in a senior facility impacted by near-roadway pollutants. The rationale for assessing the 4-day period is to corroborate the findings from RAPIDS but in a different, yet highly relevant (near-roadway), environment common in the US. The rationale for the 4-week intervention is to demonstrate for the first time that AFUs can lower exposures and improve CV endpoints over a longer-term, more clinically relevant period. The rationale for the bedroom-only AFU intervention is to show that this novel (more practical, less expensive) approach is also an effective strategy., a participant may undergo the following ordering: Block 1, bedroom AFU; Block 2, bedroom- sham filtration .

Study Participants: We will enroll n=50 participants.

Inclusion criteria: 1) Nonsmoker, 2) ≥ 60 years old, 3) residing in Carpenter Place Apartments. 4) SBP>115 mm Hg

These criteria were selected as they focus on the adverse health effects of PM2.5 on an urban/near-roadway ("vulnerable") and elderly ("susceptible") population. They are also highly responsive to the Program Announcement: *Environmental Exposures and Health: Exploration of Non-traditional Setting (PA-18-142)*.

Exclusion criteria: 1) Active cigarette smoker 2) daily secondhand smoke exposure (self-report), 3) any CV event (myocardial infarction, stroke, heart failure, revascularization) in the past 3 months, 4) unstable CV condition or risk factor (uncontrolled diabetes, class 3-4 angina or heart failure) or any medical condition that would place the participant at risk from participation or jeopardize study integrity (per investigators), 5) expected overnight travel outside their apartment during the 14-week study period, 6) unable to provide informed consent, 7) lung disease requiring oxygen, 8) renal dialysis, 9) cancer receiving active treatment or chemotherapy, 10) severe uncontrolled high BP $\geq 160/100$ mm Hg or SBP < 115 mm Hg. 11) CV medication change in the prior month. If participants are on medications for high BP, diabetes, or a CV condition, they will need to have stable therapy during the prior month with no planned changes during the study period.

Hypertension or other stable cardiometabolic risk factors or diseases are not exclusions to this trial given their prevalence in the elderly. They also enhance the sensitivity to the health impacts of air pollution and are thus important to include in the trial to assure the real-world applicability of the findings. Finally, these factors (e.g., hypertension status, basal BP, diabetes) did not modify (mitigate or augment) the BP reduction provided by AFUs in RAPIDS. We will collect complete health and medication information during screening visits and will plan subgroup and effect modification analyses by these and other key clinical characteristics.

Study location: The study will be conducted within Carpenter Place Apartments, a nonsmoking facility for low-income seniors ≥ 60 years of age. The complex houses over 150 residents and is located at [name]. We selected this site because it is important to corroborate the effectiveness of an AFU intervention at a different location from that of our initial RAPIDS trial³⁰. The facility is ideal for this renewal project (RAPIDS-2) trial because it houses low-income elderly adults (a population known to be susceptible to the health effects of PM2.5)^{1,18,19} and it is located within 150 meters of a 4-lane US highway (US-23; ~78,000 vehicles per day⁷²). Each residence consists of a one-bedroom apartment (576 sqft). Given this relatively small living space, the apartments are ideal to test the effectiveness of AFUs (positioned in the main room and/or bedroom). We have obtained approval from the management of Carpenter Place to conduct RAPIDS-2 in this facility and have observed enthusiasm from the residents regarding participation.

Pollutant levels: Preliminary data during Winter/Spring of 2018 demonstrate that this complex is impacted by near-roadway air pollutants. Average outdoor PM2.5 levels were 16.6 ± 10.7 $\mu\text{g}/\text{m}^3$. This is above AQGs and levels seen in RAPIDS in Detroit (15.7 $\mu\text{g}/\text{m}^3$) where we have already shown the benefits of lowering exposure to PM2.5 using AFUs³⁰. Traffic pollutant levels, including black carbon (1.3 ± 0.5 $\mu\text{g}/\text{m}^3$) and ultrafine particles ($10,545 \pm 2,317$ particles/cc), were also relatively high.

Recruitment: Potential participants will be recruited directly from Carpenter Place Apartments. Investigators will post fliers in public areas and investigators will hold “town-hall” style meetings to help disseminate study information. Investigators will note each resident’s status as interested, not interested, or undecided in an attempt to recruit all necessary subjects from this limited pool, and to assure residents are disturbed as little as possible. Fliers may be slid under each apartment door to reach subjects and flier information may be included in the resident newsletter.

Screening Visit: Interested individuals will contact investigators and undergo screening (fasting > 8 hours) in a private room at Carpenter Place. Information will be collected on all key demographic factors (age, race, sex), cardiometabolic risk factors (diagnosed hypertension, diabetes, hyperlipidemia), prior smoking history (pack years, when quit), and CV disease history (e.g., prior MI, stroke) as well as all medications and doses. BP and finger blood glucose (glucometer) will be measured. Urine dipstick will be performed to corroborate non-smoker status (i.e., no tobacco during past 10 days by NicAlert < 100 ng/mL). Inclusion and exclusion criteria will be reviewed and the study will be discussed in detail with each individual. Individuals who wish to participate and who satisfy all study entry criteria will sign a written informed consent document and be enrolled into the trial on a rolling basis. Height and weight will then be measured for calculation of BMI.

Study Execution: A private room in Carpenter Place will be allocated for all visits. Only one participant will be permitted in this room at any given time to protect privacy. The temperature will be maintained between 70-75 °F for all visits to limit any immediate impact on BP. ***The entire trial will be conducted within the apartment complex.***

This assures minimal risks and burden to the participants and reduces the potential impact of outdoor exposures (noise, temperature) immediately prior to study outcomes. Once enrolled, participants will be randomized into the first study block. The study consists of a 10-week, crossover trial (Fig. 5).

Activity restrictions: Participants will be provided with an activity log-sheet to record periods of: exercise, over-night stays outside their residence (if any), time periods of open outdoor apartment windows, or other concerns. We will ask participants to sleep overnight in their bedroom at Carpenter Place during all nights of the study and to notify investigators (and note in their activity log) if they must spend a night offsite. If unexpected overnight travel occurs, this will not prohibit continued participation unless they spend a total of more than 4 days during any single study block offsite. In this case the participant will discontinue the study, and their data will be excluded from analysis due to this pre-defined protocol deviation. There are no limitations on air conditioning, heating, or indoor sources of pollution (e.g., cooking). All activities will be allowed except no exercise during periods of 24-hour BP and personal PM2.5 monitoring. We will place no restrictions on opening outside apartment windows to keep the trial as real-world as possible. In RAPIDS we did not require any restriction in this regard and nevertheless we achieved the reported significant reduction in indoor/personal PM2.5 exposures and improved BP levels. Participants will be instructed to record in their logs any periods that windows were opened to facilitate determining its impact on AFU efficacy for reducing PM2.5 exposure and BP reductions in sensitivity analyses (although there were no such adverse impacts found in RAPIDS).

Visit logistics: All study visits will commence at the same time for each participant between 8AM-10AM, after fasting for >8 hours (prior to breakfast, any caffeine) and before any medications. **All BP measurements will be obtained prior to antihypertensive medications to obtain a “trough” level, per standard clinical trial practices**⁷⁰. After visits, participants will continue daily routines (and take any medications) without restrictions.

Block 1:

Week 1/day 1: An investigator will place one AFU in the bedroom of each participant's apartment. Each AFU will be set to either "active mode" (i.e., a HEPA filter inside) or "sham mode" (i.e., no HEPA filter inside) in **randomized double-blind fashion**. We have documented that both modes exhibit similar noise and identical appearance. This will be accomplished by having a different (unblinded) investigator set the AFU modes offsite beforehand – so that neither the on-site investigator nor the participants will be aware of the settings during all study blocks. This offsite unblinded investigator will be the only team member aware of the randomization order. For the **placebo intervention**: both AFUs will be set to "sham mode". The AFUs will remain running in the same mode for the entire 4-week study block.

Week 1/days 2-4: Participants will be asked to sleep every night in their own apartment and measure their blood pressure using a home BP device we provide just prior to going to bed and upon waking up. At the end of the visit on day 4, participants will have heart rate variability determined with a holter monitor for 6 minutes and blood pressure measured using the BPTru device. Subjects will be fitted with 2 portable devices: an ambulatory BP monitor and a personal PM2.5 monitor. At all times during the 24-hour period, they will wear the PM monitor or have it near them (e.g., on bedside stand while sleeping). We have demonstrated that these devices can be worn together for 24 hours without excessive burden^{38,40}. During this period, participants will be instructed not to exercise.

Week 1/day 5: Upon arrival the personal monitoring devices will be collected.

Weeks 2-3: Participants will undertake their usual activities (except for overnight travel restrictions).

Week 4: Study visit days 2-5 will be repeated as during week 1.

Visit day 5 is completed and prior to eating or taking medications, participants will have blood drawn in the study room by an investigator. An investigator will then remove the AFUs from participants' apartments.

Washout period: Participants will undergo a 1 or 2-week washout period without restrictions on activities (including overnight travel). No AFUs will be in participant's apartments during this time. We have shown in RAPIDS that a 1-week washout period is adequate, with no evidence for a carryover effect from the previous intervention on endpoints (BP, PM2.5 exposures). There was no statistically significant effect (interaction, confounding) from the order of the intervention on the results³⁰. PM2.5 exposures and BP returned to baseline after one week.

Block 2 (crossover phase): Participants will undergo the same protocol as during Block 1, the only difference being that on week 1/visit day 1 of both blocks, the AFUs will be set to different modes (active vs. sham) from prior blocks(in randomized order).

Retention plan: Based on our experience with RAPIDS, we do not anticipate retention problems. During weeks 2 and 3, investigators will contact each participant at least twice per week (phone, email, or in-person) to assure continued participation and compliant usage of AFUs, and to address any study problems.

Timeline: In RAPIDS, only 1/41 participants dropped out after enrollment. However, given the longer duration of this protocol, we intend to be realistically conservative in our estimates for RAPIDS-2. We will allow for a 10% dropout rate and thus plan to enroll 55 people to meet our goal of n=50 participants completing the entire study.

Aim 1: Determine if long-term AFU usage provides sustained reductions in PM2.5 exposure and persistent improvements in cardiometabolic outcomes.

Aim 2: Determine if nocturnal PM2.5 exposure reduction improves cardiometabolic outcomes.

Aim 3: Demonstrate the key role of adrenal activation as a novel mechanistic pathway explaining PM2.5-induced cardiometabolic effects.

Experimental Procedures and Protocols

AFU intervention: We have carefully designed this study to accommodate the needs and limitations of the volunteer subjects and minimize changes and burdens on their lifestyle by incorporating noninvasive daily home BP testing while also assuring detection of outcome-exposure associations based on our previous studies. As described above in the Progress Report section, despite the fact that the RAPIDS protocol did not restrict subjects' activities (e.g., window opening), we were able to reduce personal PM2.5 exposure and observe improved CV health outcomes. Thus, we will maintain the same protocol and study real-world exposure to the extent possible. Apartment central air conditioning and heating can be used without limitations. Participants will record in activity logs any period in which windows are opened. We will employ the same commercially available AFU brand (Holmes) proven in RAPIDS to effectively reduce indoor and personal PM2.5 exposures and lower BP among participants³⁰. For the "gold standard" comparison (2-room AFU use), we will follow the same deployment protocol successfully used in RAPIDS30 and supported by EPA guidance and expert scientific opinions⁷³⁻⁷⁶. At 8AM Monday (week 1, visit day 1) of each study block, a blinded onsite investigator will place AFUs in each participant's residence. One AFU each will be placed in both the bedroom and main living room. Each AFU will be set to the randomized mode ("active" or "sham") per the description in prior sections in a *randomized double-blind fashion* by a different offsite investigator beforehand so that neither the onsite investigator nor the participant will be aware of the settings (the HEPA filter is not visible from the outside). In both rooms the AFU will be a Holmes HAP8650B-NU-1, designed for spaces up to 310 square feet. Under the "active" mode, the AFU will be fitted with a new "true HEPA" filter (Holmes HAPF600TCS), validated to remove 99.97% of particles at 0.3 μm in size⁷³. Ultrafine (10-100 nm) particles (e.g., from traffic) and larger particles (e.g., coarse PM) are typically filtered even more effectively by HEPA filters⁷³⁻⁷⁶. Under the "sham" mode, a HEPA filter will not be installed in the AFU and there will be no significant removal of PM2.5. Each AFU will be fitted with a cumulative power consumption meter (Kill-A-Watt EZ) to verify continuous operation at the correct fan speed setting for the entire intervention period. The low noise level of the AFUs will be indistinguishable between active and sham
